Clinical study protocol

Title: A prospective, single-arm clinical trial of prevention of severe acute graft-versus-host disease after adult patients receiving allogeneic hematopoietic stem cell transplantation using a daGOAT model

Protocol number: daGOAT-adult-001

Research unit: Institute of Hematology & Blood Diseases Hospital, Chinese Academy of Medical Sciences & Peking Union Medical College.

Address: [name]

Version: 5.0

Version date: October 7, 2024

Declaration of Secrecy

This document is confidential information of Institute of Hematology & Blood Diseases Hospital, Chinese Academy of Medical Sciences & Peking Union Medical College (Tianjin, China) and is only used for the purpose of this clinical study. It shall not be disclosed to anyone other than the participating researchers and members of the institutional review board. This information cannot be used for any purpose other than the evaluation or implementation of clinical studies without the prior written consent of Institute of Hematology & Blood Diseases Hospital, Chinese Academy of Medical Sciences & Peking Union Medical College.

1. Abstract

Title	A prospective, single-arm clinical trial of prevention of severe acute graft-versus-host disease after adult patients receiving allogeneic hematopoietic stem cell transplantation using the daGOAT model
Study objective	To evaluate the efficacy and safety of ruxolitinib for prophylactic therapy of adult patients who are predicted to have a high risk for developing severe acute graft-versus-host disease (aGVHD) by the daGOAT model.
Study design	This is a prospective single-arm historical-control clinical trial. Adult patients receiving human leukocyte antigen (HLA)-mismatched allogeneic hematopoietic stem cell transplantation (allo-HSCT) will be enrolled after October 1, 2022. The propensity score matching method will be used to select controls at a ratio of 1:3 from the historical cases.
Study population	Adult patients receiving HLA-mismatched allo-HSCT.
Inclusion criteria	
1. Patients must be > 16 years of age;2. Patients receiving HLA-mismatched and non-cord blood allo-HSCT;3. Patients who can take oral medication;4. Patients have to sign an informed consent form before the start of the research procedure.
Exclusion criteria	
1. Tandem transplantation or multiple transplantations;2. Patients who are allergic to or cannot tolerate ruxolitinib;3. Mental or other medical conditions that make the patients unable to comply with the research treatment and monitoring requirements;4. Patients who are pregnant or cannot take appropriate contraceptive measures during treatment;5. Patients who are ineligible for the study due to other factors or will bear great risk if participating in the study.
Sample size	The incidence rate of severe aGVHD within 100 days of previous adult transplant patients at the Institute of Hematology & Blood Diseases Hospital, Chinese Academy of Medical Sciences & Peking Union Medical College (IHCAMS) was 18% during 1 December

	2020–31 December 2021. The incidence rate after using the daGOAT model will fall to 8% per the researchers' estimation. Comparison will be performed using a propensity score matching method to select controls at a ratio of 1:3 from the historical cases. To attain a 0.05 significance level and a 0.8 power at a presumed 5% dropout rate, \geq 102 participants will need to be enrolled, and \geq 306 historical controls will need to be matched.
Dosage regimen	
 ➤ Model-predicted high-risk patients: ruxolitinib 5mg bid po until at least day 60 post-transplant and terminated after day 100. If severe hematological signs occur such as when there is severe neutropenia ($<0.1 \times 10^9/L$), ruxolitinib can be used at half dose or discontinued as appropriate, and can continue to be used after hematology recovery. ➤ Model-predicted moderate-risk patients: ruxolitinib 2.5mg bid p po until at least day 60 post-transplant and terminated after day 100. If severe hematological signs occur such as when there is severe neutropenia ($<0.1 \times 10^9/L$), ruxolitinib can be used at half dose or discontinued as appropriate, and can continue to be used after hematology recovery. ➤ Model-predicted low risk: regular aGVHD prophylactic regimens.
Study endpoints	
Primary endpoint: incidence of severe aGVHD after transplantation within 100 days.
 
Secondary endpoints: incidence of aGVHD (any grade) in various target organs, overall survival after transplantation, relapse-free survival rate, relapse rate, incidence of severe infections, safety of treatment, and total cost of treatment.

Safety evaluation	Encompassing physical examination, vital signs, adverse events, concomitant therapy, and abnormal results of laboratory tests.
Statistical analysis	SAS and R statistical analysis software will be used to conduct the statistical analysis tailored to data properties. The propensity score matching method will be used to select controls at a ratio of 1:3 from the historical cases. Efficacy and safety variables will be compared between the two groups of the matched patients. All comparison tests will be two-sided, and statistical significance will be defined as $P < 0.05$ in all the analyses.

2. Research background

At present, there are about 40,000 new allogeneic hematopoietic stem cell transplantation (allo-HSCT) cases every year in the world ^[1, 2], among which about a quarter occur in China. Allo-HSCT has become the primary treatment method for some hematological diseases such as refractory and relapsed acute leukemia and bone marrow failure. The individuals are affected by dynamic and static multi-dimensional parameters as well as post-transplant immune reconstitution. The use of machine learning to integrate big data for predicting severe aGVHD (grade III–IV) may provide a new path towards understanding immune complications after transplantation.

Previous foundation of research

The researchers have compiled the postoperative clinical data of the patients who received HLA-mismatched allogeneic hematopoietic stem cell transplantation (allo-HSCT) at the IHCAMS from 2012 to 2021—named the ‘aGOAT dataset’, which contained 194 dynamic variables of 584 adult patients and 159 dynamic variables of 45 pediatric patients, including complete blood counts, blood biochemistry, electrolytes, cytokines, flow cytometry, antibody, fluid inflow/outflow, and vital signs. Severe aGVHD occurred within 100 days in 16% of the adult patients and 24% of the pediatric patients. A dynamic forecasting model for severe aGVHD, termed the ‘daGOAT model’, was constructed, achieving an AUROC score of more than 0.78. This result has been published in *Nature Computational Science* in 2022.^[3]

This study aims to prospectively evaluate the use of the daGOAT model in real-world clinical settings at the IHCAMS.

1. Gratwohl, A., et al., *One million haemopoietic stem-cell transplants: a retrospective observational study*. *Lancet Haematol*, 2015. 2(3): p. e91-100.

2. Xu, L.P., et al., *A review of hematopoietic cell transplantation in China: data and trends during 2008-2016*. *Bone Marrow Transplant*, 2017. 52(11): p. 1512-1518.
3. Liu, X., et al. *Dynamic forecasting of severe acute graft-versus-host disease after transplantation*. *Nat Comput Sci* , 2022.2: p. 153-159.

3. Study objective

To evaluate the efficacy and safety of ruxolitinib for prophylactic therapy of adult patients who are predicted to have a high risk for developing severe aGVHD according to the daGOAT model.

4. Study design

This is a prospective single-arm historical-control clinical trial. Adult patients receiving HLA-mismatched allogeneic hematopoietic stem cell transplantation (allo-HSCT) at the IHCAMS will be enrolled after October 1, 2022. The propensity score matching method will be used to select controls at a ratio of 1:3 from the historical cases.

The daGOAT model will dynamically predict the risk for severe aGVHD daily from day 17 to day 23 after transplantation, and medication will be adjusted according to the predicted risk.

The study flowchart is shown in Figure 1 (LR, low risk; MR, moderate risk; HR, high risk).

[figure not shown]

Figure 1. Study flowchart

5. Study population

Adult patients receiving HLA-mismatched allo-HSCT from the IHCAMS.

5.1 Inclusion criteria

- 1) Patients must be > 16 years of age;
- 2) Patients receiving HLA-mismatched and non-cord blood allo-HSCT;
- 3) Patients who can take oral medication;
- 4) Patients have to sign an informed consent form before the start of the research procedure.

5.2 Exclusion criteria

Patients who meet any of the following criteria will not be enrolled in the study:

- 1) Tandem transplantation or multiple transplantations;
- 2) Patients who are allergic to or cannot tolerate ruxolitinib;
- 3) Mental or other medical conditions that make the patients unable to comply with the research treatment and monitoring requirements;
- 4) Patients who are pregnant or cannot take appropriate contraceptive measures during treatment;
- 5) Patients who are ineligible for the study due to other factors, or will bear great risk if participating in the study.

5.3 Drop-out and withdrawal criteria

- 1) Failure of neutrophil engraftment within 30 days of transplantation;
- 2) A patient may withdraw from the study if he/she does not wish to continue participating in the study, and the date and reason for withdrawal shall be recorded. The investigator may also decide to discontinue a patient from the clinical study if there is an unacceptable risk.

6. Dosage regimen

- 1) Model-predicted high-risk patients: ruxolitinib 5mg bid po until at least day 60 post-transplant and terminated after day 100. If severe hematological signs occur such as when there is severe neutropenia ($<0.1 \times 10^9/L$), ruxolitinib can be used at half dose or discontinued until recovery.

- 2) Model-predicted moderate-risk patients: ruxolitinib 2.5mg bid. po until at least day 60 post-transplant and terminated after day 100. If severe hematological signs occur such as when there is severe neutropenia ($<0.1 \times 10^9/L$), ruxolitinib can be used at half dose or discontinued until recovery
- 3) Model-predicted low risk: regular aGVHD prophylactic regiments.

7. Study assessment and follow-up

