7.3. Laboratory tests

Laboratory tests performed at diagnosis and before and after transplantation at various time points.

- 1) Blood routine: Red blood cell count, hemoglobin, platelet count, white blood cell count, white blood cell classification count, etc.
- 2) Urine routine: specific gravity, pH, urine sugar, urine protein, urobilinogen, ketone bodies, microscopic red blood cells, urine white blood cells, bacteria, crystals, tube type, etc.
- 3) Coagulation function tests: activated partial thromboplastin time, plasma prothrombin time, international normalized ratio of prothrombin time, thrombin time, plasma fibrinogen, and plasma D-dimer.
- 4) Bone marrow:
 - Smear or biopsy analysis;
 - Immunophenotype analysis by flow cytometry;
 - Chromosome karyotype;
 - Gene mutation analysis.

5) Blood biochemistry.

- Electrolyte includes sodium, potassium, chlorine, calcium and phosphorus, etc.
- Liver function tests include alanine aminotransferase, aspartate aminotransferase, alkaline phosphatase, γ -glutamyltransferase, lactate dehydrogenase, total protein, albumin, total bilirubin, direct bilirubin, total cholesterol, triglyceride, etc.
- Renal function tests include blood urea nitrogen, uric acid and creatinine, etc.

6) Immune cell subset analysis by flow cytometry.

7.4. Other examinations.

- 1) 12-lead electrocardiogram;
- 2) Chest computed tomography;
- 3) Abdominal ultrasound and abdominal CT when necessary;
- 4) Echocardiography when necessary.
- 5) Other examinations that the investigators consider appropriate.

7.5. Follow-up.

Patients will be followed up at days 14, 28, 42, 60, 90, 180, 270, 360 and 540 after transplantation; data on infection, relapse, survival, and quality of life will be collected.

8. Study endpoints

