8.1 Primary endpoint

Incidence of severe aGVHD after transplantation within 100 days.

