8.2 Secondary endpoints

Incidence of aGVHD (any grade) in various target organs, overall survival after transplantation, relapse-free survival rate, relapse rate, incidence of severe infections, safety of treatment, and total cost of treatment.

9. Adverse event and severe adverse event

Starting from the date of signing the informed consent form until the last visit, all adverse events will be evaluated and recorded according to the Common Terminology Criteria for Adverse Events version 5.0.

10. Sample size calculation

The incidence rate of severe aGVHD within 100 days of previous adult transplant patients at the IHCAMS was 18% during 1 December 2020 – 31 December 2021. The incidence rate after using the daGOAT model will fall to 8% per the researchers' estimation. Comparison will be performed using a propensity score matching method to select controls at a ratio of 1:3 from the historical cases. To attain a 0.05 significance level and a 0.8 power at a presumed 5% dropout rate, ≥ 102 participants will need to be enrolled, and ≥ 306 historical controls will need to be matched.

11. Statistical analysis

SAS and R statistical analysis software will be used to conduct the statistical analysis tailored to data properties. The propensity score matching method will be used to select controls at a ratio of 1:3 from the historical cases. Efficacy and safety variables will be compared between the two groups of the matched patients. All comparison tests will be two-sided, and statistical significance will be defined as $P < 0.05$ in all the analyses.

12. Ethical review

The study will be conducted in accordance with the Declaration of Helsinki (2013), relevant regulations issued by the government of the People's Republic of China, and additional precautions required by the ethics review committee at the IHCAMS.

Before the study, the investigator will obtain approvals from the ethics review committee at the IHCAMS regarding the study protocol data sheet, informed consent form, subject enrollment form, and other relevant information to be provided to the subject before enrollment. During the study, if there is any amendment to the study protocol data sheet, informed consent form, subject enrollment form, and other relevant information to be provided to the subject before enrollment, renewed approvals shall be obtained from the IHCAMS ethics review committee before continuation of the study.

13. Preservation of research data

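### Section 5.3(1) makes non-engraftment by day 30 a drop-out criterion, after model-guided ruxolitinib can start, without saying that these patients stay in follow-up and analysis

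*Protocol*

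**What the plan says.** Section 5.3 (Drop-out and withdrawal criteria) gives as its first item: "Failure of neutrophil engraftment within 30 days of transplantation". Exclusion before enrolment is covered separately in 5.2, so this item applies to patients already in the trial. The second item covers voluntary withdrawal, for which "the date and reason for withdrawal shall be recorded", and adds: "The investigator may also decide to discontinue a patient from the clinical study if there is an unacceptable risk".

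Section 4 sets the timing of the intervention: "The daGOAT model will dynamically predict the risk for severe aGVHD daily from day 17 to day 23 after transplantation", with medication adjusted to the predicted risk. Section 6 continues ruxolitinib to at least day 60 in moderate- and high-risk patients. It deals with severe neutropenia on the drug separately: "ruxolitinib can be used at half dose or discontinued until recovery".

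The primary endpoint (8.1) is "Incidence of severe aGVHD after transplantation within 100 days". Section 7.5 states: "Patients will be followed up at days 14, 28, 42, 60, 90, 180, 270, 360 and 540 after transplantation". Section 10 sets the sample size "at a presumed 5% dropout rate", giving at least 102 participants and 306 matched historical controls. Section 11 compares the two groups of matched patients. No section says what happens to the data of a patient who meets 5.3(1).

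**The concern.** The day-30 criterion is judged after the model has classified patients and treatment can have begun. If meeting it takes a patient out of follow-up and analysis, the trial-group rate is estimated only in those who engrafted by day 30. That is selection on a post-treatment event. Propensity matching on baseline variables balances what was known before treatment and cannot undo it. Nothing in the protocol says that historical controls must also have engrafted by day 30, so the two groups could be selected differently.

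The outcome that triggers the rule may also be related to the drug, since section 6 foresees severe neutropenia on ruxolitinib. That link is limited. Neutropenia on treatment is not the same event as failure to engraft, and the drug could matter only for moderate- or high-risk patients who had not yet engrafted when it started. The documents do not give their number.

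The primary endpoint is at stake, and so are the survival, relapse, severe-infection and safety comparisons, from which the same patients would be missing.

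**Working it through.** **1. Timing (sections 4, 5.3, 7.5, 8.1).**
- From the prediction window to the criterion: 30 - 23 = 7 days to 30 - 17 = 13 days.
- Primary-endpoint window left after day 30: 100 - 30 = 70 of 100 days.
- Scheduled visits after day 30: days 42, 60, 90, 180, 270, 360 and 540, which is 7 of 9.

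The protocol gives no explicit first-dose day. That treatment can start on days 17-23 follows from section 4.

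**2. How section 10 treats drop-outs.** Inputs: 8% against 18%, 1:3, two-sided 0.05 (section 11), power 0.80, 5% dropout. The formula is not stated. The unpooled two-proportion formula reproduces the figure:

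n = (0.08 × 0.92 + 0.18 × 0.82 / 3) × (1.960 + 0.842)² / 0.10² = 0.1228 × 7.849 / 0.01 = 96.4

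96.4 / 0.95 = 101.5, rounded up to 102, and 3 × 102 = 306. Multiplying instead gives 96.4 × 1.05 = 101.2, also 102. The two-sided pooled (124.1) and arcsine (114.2) versions before inflation do not lead to 102. The target therefore assumes about 97 evaluable patients out of 102, so drop-outs in general are counted as lost. Non-engraftment is not named there.

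**3. Shift in the trial-group primary rate.** Let d be the fraction dropped, p the true rate in all enrolled, and r the risk of severe aGVHD in those dropped. The rate in those remaining is (p - d·r)/(1 - d), so the shift is d(p - r)/(1 - d). The documents give neither d nor r. Assumed ranges: d = 1-5% (about 1-5 of 102 patients) and r = 0-50%.

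| p | d | r = 0 | r = 50% |
|---|---|---|---|
| 8% | 1% | +0.08 | -0.42 |
| 8% | 5% | +0.42 | -2.21 |
| 18% | 1% | +0.18 | -0.32 |
| 18% | 5% | +0.95 | -1.68 |

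Units are percentage points. For example, 0.05 × (0.08 - 0.50) / 0.95 = -0.0221. When r = p the shift is zero. A negative shift flatters the trial group and a positive one counts against it.

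**4. Effect on a false claim of benefit.** Take a true rate of 18% in both groups, controls not selected on engraftment, and the uncorrected chi-square test at two-sided 0.05. The exact probability of a significant result favouring the trial is:
- 5% dropped (97:291): 2.3% with no selection, 1.4% if r = 0, 5.1% if r = 50%.
- 1% dropped (101:303): 2.2%, 2.0% and 2.6%.

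The 5% inflation in section 10 restores numbers. It does not remove a shift of this kind. Effects on survival, infection and safety cannot be computed, because the documents give no inputs.

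**The case against.** A reader might infer that the protocol removes these patients from follow-up and analysis. It does not say so. The references to the clinical study and to recording date and reason both stand in 5.3(2), which concerns voluntary withdrawal and the investigator's decision, not non-engraftment. A planning allowance for dropout is not a rule that ends data collection. The schedule in 7.5 makes no exception for drop-outs, and section 9 records adverse events until the last visit. All of this stands, and loss to follow-up is therefore an inference. It remains the more natural reading of an item listed under drop-out criteria, given that section 6 handles interruption of the drug separately. Neither 7.5 nor section 9 expressly covers a dropped patient.

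It can also be said that analysis sets belong in a SAP, which may exist. That is fair for the analysis set. A SAP cannot, however, recover data that were not collected because a protocol rule ended follow-up, and the rule itself is in the protocol.

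Finally, the larger shifts come from extreme assumptions. The -2.2 figure places 0.05 × 0.50 / 0.08 = 31% of all severe aGVHD in 5% of patients, and nothing in the documents supports such concentration. This too stands. The upper ends are bounds on the assumed range, not expectations.

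**Conclusion.** The point holds as a drop-out rule that needs correcting. Followed as it most naturally reads, 5.3(1) selects trial patients on an event 7-13 days after model-guided treatment can begin and 70 days before the primary endpoint closes. Baseline matching cannot repair that.

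The size is probably small. Under the assumed 1-5% dropped and 0-50% risk, the shift lies between +0.4 and -2.2 points at a true rate of 8%, and between +0.9 and -1.7 points at 18%, against a planned difference of 10. At 1% dropped it is under half a point either way. These figures assume that follow-up ends at day 30 and that controls are not selected on engraftment. The documents state neither.

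A reader might infer that the rule biases the trial towards benefit, or that it roughly doubles the false-benefit probability. The documents support neither. The direction depends on whether dropped patients have a higher or lower risk than the rest, which is not given, and the 5.1% figure arises only at the extreme of both assumptions.

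This should be fixed because the remedy is cheap. Confidence is medium, since the end of follow-up is inferred.

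**What to change.** State in 5.3 that failure to engraft by day 30 does not end data collection. These patients should stay in the scheduled follow-up and in the primary, survival, infection and safety comparisons unless they withdraw consent. This concerns data only; treatment decisions are not addressed.

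As a fallback, if an engraftment condition is kept for any analysis, apply the same day-30 condition to the historical controls, label that analysis as secondary, and acknowledge that it still conditions on a post-treatment event.

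The cost is a sentence or two in 5.3 and follow-up of a few more patients, about 1-5 under the assumed range.

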7.1. Medical history

Medical history (previous treatments, including chemotherapy).

7.2. Physical examination

Physical examination before transplantation, including body height, body weight, body surface area, and the Eastern Cooperative Oncology Group score.

7.3. Laboratory tests

Laboratory tests performed at diagnosis and before and after transplantation at various time points.

- 1) Blood routine: Red blood cell count, hemoglobin, platelet count, white blood cell count, white blood cell classification count, etc.
- 2) Urine routine: specific gravity, pH, urine sugar, urine protein, urobilinogen, ketone bodies, microscopic red blood cells, urine white blood cells, bacteria, crystals, tube type, etc.
- 3) Coagulation function tests: activated partial thromboplastin time, plasma prothrombin time, international normalized ratio of prothrombin time, thrombin time, plasma fibrinogen, and plasma D-dimer.
- 4) Bone marrow:
 - Smear or biopsy analysis;
 - Immunophenotype analysis by flow cytometry;
 - Chromosome karyotype;
 - Gene mutation analysis.

5) Blood biochemistry.

- Electrolyte includes sodium, potassium, chlorine, calcium and phosphorus, etc.
- Liver function tests include alanine aminotransferase, aspartate aminotransferase, alkaline phosphatase, γ -glutamyltransferase, lactate dehydrogenase, total protein, albumin, total bilirubin, direct bilirubin, total cholesterol, triglyceride, etc.
- Renal function tests include blood urea nitrogen, uric acid and creatinine, etc.

6) Immune cell subset analysis by flow cytometry.

7.4. Other examinations.

- 1) 12-lead electrocardiogram;
- 2) Chest computed tomography;
- 3) Abdominal ultrasound and abdominal CT when necessary;
- 4) Echocardiography when necessary.
- 5) Other examinations that the investigators consider appropriate.

7.5. Follow-up.

Patients will be followed up at days 14, 28, 42, 60, 90, 180, 270, 360 and 540 after transplantation; data on infection, relapse, survival, and quality of life will be collected.

8. Study endpoints

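### Does leaving aGVHD and a day-100 contact out of section 7.5 mean that the trial arm and the historical controls will be graded and dated differently?

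*Protocol*

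**What the plan says.** The primary endpoint in section 8.1 is "Incidence of severe aGVHD after transplantation within 100 days". Among the secondary endpoints, section 8.2 lists "Incidence of aGVHD (any grade) in various target organs". The only explanation of severe is in section 2, which equates it with grade III–IV and names no grading system.

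Section 7.5 sets the schedule: "Patients will be followed up at days 14, 28, 42, 60, 90, 180, 270, 360 and 540 after transplantation". It then states that "data on infection, relapse, survival, and quality of life will be collected". Neither aGVHD nor day 100 appears.

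Section 9 has adverse events recorded over a continuous period: "Starting from the date of signing the informed consent form until the last visit". It adds that "all adverse events will be evaluated and recorded according to the Common Terminology Criteria for Adverse Events version 5.0".

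The comparison is with historical cases from the same hospital, matched 1:3 by propensity score. Under section 11, "Efficacy and safety variables will be compared between the two groups of the matched patients". No sentence says how aGVHD grade and onset date are to be taken from the controls' records.

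**The concern.** The section headed follow-up names days and items but omits the primary outcome, and the day that closes the outcome window falls in a gap between two visits. The one grading standard in the document, CTCAE 5.0, is tied neither to grade III–IV nor to organ stage.

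In a randomised trial, a loosely stated outcome rule would normally act on both arms alike. Here the arms differ in how they are observed. Trial patients have a prospective record from consent, while the controls have only what the hospital wrote at the time. Propensity matching balances baseline covariates and cannot repair a difference in how the outcome is classified. If severe cases were counted less completely in the trial arm, a null treatment could look beneficial. If they were counted more completely there, under closer observation, a real benefit could be missed.

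**Working it through.** **Which parts of the Protocol bear on capture of the endpoint**

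- *Is section 7.5 the complete list of endpoint data?* No. It leaves out total cost of treatment, which is a secondary endpoint in section 8.2, and includes quality of life, which is not an endpoint at all. Absence from this list therefore does not mean that an item goes uncollected.
- *Are onsets on days 91–100 lost?* Section 9 runs without a break from consent to the last visit. An episode in that interval can be captured there or in hospital records and dated afterwards. The missing day-100 contact does not by itself lose an event.
- *Does CTCAE grade the endpoint?* Section 9 concerns adverse events. It does not say that aGVHD for section 8 is graded by CTCAE, so there is no contradiction with grade III–IV.
- *Could the hospital classify historical patients?* Yes. Section 2 reports severe aGVHD within 100 days in 16% of the 584 adults in the 2012–2021 dataset. Section 10 reports 18% for December 2020 to December 2021, again within 100 days. The prediction model was built on that dataset, so severe cases had to be identified in it. The Protocol does not state that the matched controls come from exactly these patients, but hospital, term and window are the same.

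**The plan's own figure**

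Inputs from section 10: 8% versus 18%, ratio 1:3, level 0.05 (two-sided by section 11), power 0.80, dropout 5%. With unpooled variance:

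n = (1.960 + 0.842)² × (0.08 × 0.92 + 0.18 × 0.82 / 3) / 0.10² = 96.4

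96.4 / 0.95 = 101.5, so 102 participants, and 3 × 102 = 306 controls. The stated size is reproduced.

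**What unequal classification could do (illustration only)**

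Evaluable patients: 102 × 0.95 = 96.9, taken as 97, and 97 × 3 = 291 controls. The test is assumed, since section 11 names none: Pearson chi-square without continuity correction, two-sided 0.05, exact binomial rejection probabilities. The errors are assumed and relative.

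| Assumed error | Observed rates, trial v control | Result |
|---|---|---|
| None, true benefit | 8% v 18% | power 69.6% |
| Trial arm over-counted 10% | 8.8% v 18% | power 60.6% |
| Trial arm over-counted 20% | 9.6% v 18% | power 51.4% |
| Trial arm over-counted 50% | 12% v 18% | power 27.0% |
| None, no true effect | 18% v 18% | false positives for benefit 2.3% |
| Trial arm under-counted 10% | 16.2% v 18% | false positives for benefit 5.4% |
| Trial arm under-counted 20% | 14.4% v 18% | false positives for benefit 11.5% |

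If both groups carry the same 20% error, the benefit-direction false-positive rate stays at 2.1% (under) or 2.3% (over), with power 56.9% or 79.8%.

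Error confined to the controls also matters. By the pooled normal approximation, with a true 8% versus 18%, missing 10%, 20% or 30% of control cases lowers power from 68% to 52%, 36% or 21%.

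At the full 102 versus 306 the pattern is the same. Power is 71.8%, falling to 53.3% or 28.0% with 20% or 50% over-counting in the trial arm. False positives for benefit are 2.2%, rising to 5.4% or 11.7% with 10% or 20% under-counting.

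The starting power of about 70%, against the planned 80%, comes from the pooled test assumed here and has nothing to do with classification. For scale, 97 × 0.18 = 17.5 severe cases, so a 20% under-count is 17.5 × 0.2 = 3.5 cases.

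**The case for a change.** The strongest case for a change is that visit schedules and outcome criteria are protocol content and need not wait for an analysis plan. With historical controls, equal classification of the outcome is the safeguard that matching cannot give, and the illustration shows that three or four differently graded patients could multiply the false-positive rate about fivefold (11.5 / 2.3 = 5.0). Adding onset date, organ stage and maximum grade on one named scale, with a chart check at day 100 and the same abstraction for controls, would settle it without touching the endpoint or any visit.

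The factual part stands: section 7.5 does not list aGVHD, no scale is named, and no rule for common abstraction is written. The sensitivity to unequal grading is real too.

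What does not stand is the step to a defect. The argument shows that comparability is not written down; it does not show that any rule in the plan yields the wrong classification. The lack of a prospective record for controls is a property of every historical comparison. The remedy is also less light than it looks. It means organ-stage abstraction for about 306 controls and for patients already enrolled (1 October 2022 to 7 October 2024 is 737 days), plus renewed ethics approval under section 12.

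A further suggestion, to report severe aGVHD through day 180 in both groups, addresses whether disease is prevented or merely delayed. That is a separate question, and the Protocol does not show that control records could support the analysis.

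**Conclusion.** No change to the plan follows. The gap is an unwritten grading and abstraction rule, which the investigators can be expected to fill with the classification that the hospital already uses for severe aGVHD within 100 days. Naming the scale and listing aGVHD in section 7.5 would be a reasonable clarification, but it would not correct a rule shown to give a wrong result.

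The size of any bias is unknown, and so is its direction. The figures of 11.5% for false positives and 51% for power at a 20% relative error rest on error rates and a test that the Protocol does not supply; they measure sensitivity only. The conclusion assumes that the same hospital applies the same meaning of grade III–IV and the same 100-day window to both groups. The Protocol's text is consistent with this, though no sentence requires it. Evidence that controls had been graded on another scale, or could not be graded from their records, would reopen the point.
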